NCT04347122

Tranexamic Acid in Radical Resection and Endoprosthetic Reconstruction Protocol

Dec 17, 2019

University of Kansas Medical Center
RESEARCH PROTOCOL INVOLVING HUMAN SUBJECTS TEMPLATE
WITH GUIDANCE

Version date: 12/17/2019

Principal Investigator: [name] MD, Assistant Professor of Orthopaedic Surgery

Study Title: Tranexamic Acid in Radical Resection and Endoprosthetic Reconstruction: A Randomized Controlled Trial

Co- Investigator(s): [name] MD, [name] MD, [name] MD

I. Purpose, Background and Rationale A. Aim and Hypotheses

Resection of bony and soft tissue tumors with endoprosthetic reconstruction presents a significant risk of perioperative blood loss requiring transfusion. As transfusions are known to have inherent risks, a goal of therapy is to minimize perioperative blood loss. Tranexamic acid (TXA) is an antifibrinolytic that is commonly used to reduce blood loss in orthopaedic procedures, most often arthroplasty. The safety (even in patients with significant comorbidities) and efficacy of TXA in joint arthroplasty is well documented in the literature. There is, however, a dearth of literature exploring the safety and efficacy of TXA in musculoskeletal oncologic patients.

The aim of this study is to determine in a randomized controlled fashion if there is any difference in perioperative blood loss and blood transfusion rates when tranexamic acid is used compared to when it is not used in patients undergoing radical resection of bone and soft tissue sarcomas with endoprosthetic reconstruction. Hypotheses: (1) TXA will decrease perioperative blood loss. (2) TXA will decrease blood transfusion rates. (3) TXA will decrease post-operative surgical drain output.

B. Background and Significance

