is not used in patients undergoing radical resection of bone and soft tissue sarcomas with endoprosthetic reconstruction. Statement of Purpose: to determine in a randomized controlled fashion if there is any difference in perioperative blood loss and blood transfusion rates following radial resection of malignant bony tumors with endoprosthetic reconstruction when TXA is used compared to when it is not. Primary outcome measure: determination of perioperative blood loss. To do this, values will be recorded preoperatively and compared to post-operative values. Perioperative blood loss will be calculated using the Hemoglobin balance method.²³⁻²⁶ Secondary outcome measures: (1) Blood transfusion rates. (2) Surgical drain output.

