B. Study Type and Design: Type of Study: multi-center prospective randomized controlled trial. Study Design: We will initially monitor 4 groups of patients. The first group (20 patients) will undergo bony tumor resection of the femur or proximal tibia and endoprosthetic reconstruction with TXA. The second group (20 patients) will undergo bony tumor resection of the femur or proximal tibia and endoprosthetic reconstruction without TXA. The third group (50 patients) will undergo soft tissue sarcoma resection of the lower extremity with TXA. The fourth group (50 patients) will undergo soft tissue sarcoma resection of the lower extremity without TXA. The use of TXA is well established for arthroplasty at this institution given the body of evidence supporting both efficacy and safety. Treatment assignments will be stratified by type of resection location. Patient randomization will be done via randomization program through REDCap. The randomization process will be performed centrally at Kansas University Medical Center and the treating surgeon will not have access to the randomization list. Randomization will occur prior to definitive surgical procedure, and the treating surgeon and pharmacy will be notified to ensure adequate vials of tranexamic acid are available in the operating room (investigators/surgeons are not blinded). Patients will be blinded to treatment allocation. Those in groups using TXA will receive 1g TXA IVPB 10 minutes prior to incision and a second dose of 1g IVPB at the time of closure which is the standard protocol used for total joint arthroplasty. The TXA will be administered by the anesthesia team. If the surgeon determines intraoperatively that TXA is required for patient safety, the drug should be used. Patients receiving a non-standard dosing of TXA will then be excluded from the study. Routine hemoglobin and hematocrit measurements will be observed preoperatively as well as postoperatively at 6 hours and in the mornings of postoperative days 1-3. This laboratory regimen is currently the standard of care and utilized routinely. Patients may be discharged prior to obtaining all 4 blood draws. If a patient is discharged prior to postoperative day 3, no additional blood draw will be performed. Additionally, both intraoperative and postoperative incidents of blood transfusion will be monitored to calculate transfusion rates. Postoperative erythrocyte transfusions will be given for hemoglobin below 7.0 as is the current practice guidelines used by the attending surgeons at this institution. Other facilities are encouraged to follow this protocol, however, the ultimate decision for blood transfusion will be at the discretion of the treating physician. Surgical drains are also used routinely and their daily output will be recorded until they are deemed appropriate to pull by the attending surgeon. Patients will be clinically monitored daily while in the hospital and in subsequent follow up visits for symptoms of DVT or embolism and appropriate diagnostic screening with venous Doppler will be utilized if symptoms are present, as is also part of current routine postoperative care. Our DVT prophylaxis protocol postoperatively will be 4 weeks of aspirin 81 mg BID unless medical co-morbidities necessitate the use of other anti-coagulation. Mechanical DVT prophylaxis in the form of sequential compression devices will also be

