
utilized. We also plan to record patient specific factors including age, sex, smoking status, BMI, pre-op diagnosis, operative time, comorbidities, and length of stay. These variables will be analyzed independently to detect any correlation with perioperative blood loss and erythrocyte transfusion rate.

C. Sample size, statistical methods, and power calculation

Method of Randomization: Patient randomization will be done via a randomization program through REDCap. The randomization process will be performed centrally at Kansas University Medical Center and the treating surgeon will not have access to the randomization list. Randomization will occur prior to definitive surgical procedure, and the treating surgeon and pharmacy will be notified to ensure adequate vials of tranexamic acid are available in the operating room (investigators/surgeons are not blinded). Patients will be blinded to treatment allocation. Treatment assignments will be stratified by type of resection. A power of 0.9 would require a total of 40 patients (20 per treatment group) be enrolled in the bony tumor group and 100 patients (50 per treatment group) in the soft tissue tumor group.

Since we are gathering entirely objective data the treating surgeon does not need to be blinded. Group differences in preoperative hemoglobin and hematocrit, transfusion requirements, drain output at 24 hours, and changes in hemoglobin and hematocrit will be compared using pairwise Student T-test analysis. Pairwise T-tests between each of the groups (for continuous variables) and Chi squared analysis (for categorical variables) will be used to determine if a statistically significant difference exists between the groups in terms of the patient specific factors that are also collected and analyzed (age, sex, smoking status, BMI, operative time, length of stay).

D. Subject Criteria (See Vulnerable Populations appendix, if applicable):

Inclusion criteria: Patients (male or female) between the ages of 18-90 undergoing wide resection of a malignant bony tumor of the lower extremity with endoprosthetic reconstruction or resection of soft tissue sarcoma measuring >5cm.

Exclusion criteria:

- Patients undergoing revision endoprosthetic reconstruction
- Patients with known coagulopathy
- Known history of DVT or embolic disease
- Benign tumors
- Patients with allergy to TXA
- Those refusing blood products
- Those concurrently on anti-coagulant therapy
- Pregnant and nursing women

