1. Describe steps to be taken to assure that the data collected are accurate, consistent, complete and reliable. (source data verification, audits or self – assessment) Source data verification and self-audits will be performed. The protocol for the clinical trial will be spelled out for the participants. A discussion will be had between the PI at KUMC and the PI at the participating institution to ensure the protocol is understood.

V. Data Analysis and Reporting

A. Statistical and Data Analysis: Group differences in preoperative hemoglobin and hematocrit, transfusion requirements, drain output at 24 hours, difference in hemoglobin balance method, and changes in hemoglobin and hematocrit will be compared using pairwise Student T-test analysis. Pairwise T-tests between each of the groups (for continuous

variables) and Chi squared analysis (for categorical variables) will be used to determine if a statistically significant difference exists between the groups in terms of the patient specific factors that are also collected and analyzed (age, sex, smoking status, BMI, operative time, length of stay, presence of coagulopathy, specific anticoagulation regimen should it differ from study protocol, size of resection, depth of resection, location of tumor, pathologic diagnosis, stage of disease).

B. Outcome: We expect the results to be similar to the TXA arthroplasty studies/literature with regards to decreased perioperative blood loss and decreased transfusion rates. There are not necessarily any criteria for success or failure. The results of this study will help provide a definitive answer regarding the safety and efficacy of TXA in oncologic patients. This will help unify the musculoskeletal oncology field in their use or abandonment of TXA.

C. Study results to participants: The study results/conclusions will not be given to subjects unless they are specifically asked for at future scheduled outpatient clinic visits. Once the proposed study is completed a conversation with subjects can occur on an outpatient basis at their routine scheduled clinic visits regarding our results and conclusions if desired. The subjects reserve the right to know what conclusions were drawn from the study they directly participated in. In addition, we plan to publish a manuscript with our results/conclusions after completion of the study which can be sought after if desired.

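### Outcomes are compared by unadjusted t-tests that use neither preoperative hemoglobin nor the randomisation stratum, and the transfusion rate has no analysis of its own

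*Combined protocol and SAP*

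**What the plan says.** Section II.B sets up four groups: bone resection with and without TXA (20 each) and soft tissue sarcoma resection with and without TXA (50 each). Section II.C states "Treatment assignments will be stratified by type of resection"; II.B words the stratum slightly differently, adding location. Each stratum is sized on its own. For bone, II.C says "A power of 0.9 would require a total of 40 patients (20 per treatment group) be enrolled in the bony tumor group". For soft tissue, it sets 50 per arm at the same power, 100 in all.

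The outcome analysis is one sentence, given in II.C and again in V.A. It lists preoperative hemoglobin and hematocrit, transfusion requirements, 24-hour drain output and the hemoglobin and hematocrit changes. Only V.A adds the primary outcome, blood loss by the hemoglobin balance method: "difference in hemoglobin balance method, and changes in hemoglobin and hematocrit will be compared using pairwise Student T-test analysis". The pairs are not named and no covariate is mentioned.

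Chi-squared appears in the next sentence, where the tests are "used to determine if a statistically significant difference exists between the groups in terms of the patient specific factors". Transfusion is not in that list of factors in either section.

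Hypothesis 2 in I.A is "TXA will decrease blood transfusion rates". II.A has "Secondary outcome measures: (1) Blood transfusion rates", and II.B says "both intraoperative and postoperative incidents of blood transfusion will be monitored to calculate transfusion rates".

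**The concern.** The plan collects the stratum and preoperative hemoglobin and then uses neither to sharpen the estimate of the TXA effect. Preoperative hemoglobin is itself t-tested between randomised arms, which says nothing about TXA. It could instead explain part of the variation in blood loss, and that matters most in the 40-patient bone stratum. No section gives a TXA effect across both strata, although the three hypotheses are not divided by tumour type and V.B looks to a definitive answer for oncologic patients.

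The transfusion rate is a different kind of gap. II.B builds it from transfusion incidents, so it is naturally a proportion. The analysis text replaces it with transfusion requirements, which could mean yes/no, incidents or units. As written, whoever runs the analysis must choose both the measure and the test for a named hypothesis.

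**Working it through.** **Inputs.** From the plan: 20 + 20 bone, 50 + 50 soft tissue, power 0.9 in each stratum (II.C). The plan gives no alpha, effect, SD, correlation or transfusion proportion. Assumed here: two-sided 0.05; correlation rho between preoperative hemoglobin and blood loss of 0 to 0.5; bone SD one to three times soft tissue SD; proportion transfused 10% to 50%.

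**1. The plan's own sizes.** They cannot be reproduced without an effect and SD, so I solved backwards. Noncentral-t power of 0.90 with 20 per arm requires a standardised effect d = 1.052; with 50 per arm, d = 0.655.

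**2. Adjusting for preoperative hemoglobin within each stratum.** ANCOVA multiplies residual variance by 1 − rho², so d becomes d/√(1 − rho²), with one degree of freedom lost. For example, at rho = 0.5 in bone: 1.052/√0.75 = 1.215.

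| rho | Bone, formula | Soft tissue, formula | Bone, simulated | Soft tissue, simulated |
|---|---|---|---|---|
| 0 | 0.900 | 0.900 | 0.893 | 0.895 |
| 0.1 | 0.902 | 0.903 | 0.895 | 0.904 |
| 0.3 | 0.924 | 0.925 | 0.916 | 0.923 |
| 0.5 | 0.962 | 0.963 | 0.958 | 0.962 |

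The simulation (20,000 trials) draws the covariate at random, so it includes the cost of chance imbalance. The largest loss is 0.900 − 0.893 = 0.007. There is nothing to gain at rho = 0.1 in bone; the gain becomes visible from about 0.3.

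**3. Overall TXA contrast adjusted for stratum.** Weight each stratum by half its per-arm size, 10 and 25. With bone SD equal to k times soft tissue SD and the same standardised effects, the expected test statistic is (10 × 1.052k + 25 × 0.655)/√(10k² + 25). Drop one term of the numerator if the effect is in one stratum only.

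- k = 1, both effects real: 26.9/5.92 = 4.5, power about 0.99.
- k = 1, bone only: 10.52/5.92 = 1.78, power 0.42. Soft tissue only: 16.4/5.92 = 2.77, power 0.78.
- k = 2: bone only 21.04/8.06 = 2.61, power 0.74. Soft tissue only 16.4/8.06 = 2.03, power 0.53.
- k = 3: bone only 31.56/10.72 = 2.94, power 0.84. Soft tissue only 16.4/10.72 = 1.53, power 0.33.

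The k = 1 powers use the t distribution and the others a normal approximation. With both effects real, power stays near 0.99 throughout. With one effect real, the ordering of the two strata reverses as k grows.

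**4. Transfusion as a proportion.** With equal proportions p in both arms and both strata, the 95% half-width of a Mantel-Haenszel risk difference is 1.96 × √(2p(1 − p)/70). This gives 0.10, 0.15 and 0.17 at p = 10%, 30% and 50%. These figures show the precision to expect; they do not measure harm from the present wording.

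**The case against.** The best defence is that separate analysis was the design. The two strata are different operations, each has its own sample size, and an unadjusted t-test between randomised arms is valid. The aim in I.A even speaks only of resection with endoprosthetic reconstruction, and an overall estimate weighted as above would take 25/35 = 71% of its weight from soft tissue. This stands, and it is why the overall effect belongs in a supporting role.

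A second defence is that the hemoglobin balance calculation already uses preoperative values (II.A). That builds them into the outcome; it is not covariate adjustment, and they may still predict the calculated loss. It is fair to add that the correlation is undocumented and the gain may be nil.

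A third is that chi-squared for categorical variables covers transfusion. A reader may suppose so, but the sentence confines it to patient factors.

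Stronger readings should be resisted:

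- A reader might infer that t-tests among all six pairs of groups are planned for the outcomes. The phrase about each of the groups belongs to the patient factors, and the per-stratum sizing points to two contrasts.
- A reader might treat the missing alpha and split-result rule as the main fault. Two tests at 0.90 power give exactly one significant result with chance 2 × 0.9 × 0.1 = 0.18 under any such plan. The 1 − 0.95² = 0.0975 chance of a false positive is a problem only if either stratum may count as proof for both. Separate sizing fits separate claims.
- A reader might say a t-test on transfusion requirements cannot address the rate. If the item were coded yes/no, it would compare proportions. The defect is that the measure is undefined.

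**Conclusion.** The point holds as a should-fix matter of efficiency and completeness; it does not make the planned tests invalid. No section supplies a covariate-adjusted analysis, a stratum-adjusted TXA effect or a stated analysis of the proportion transfused.

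The precision at stake is modest to useful: per-stratum power of about 0.90, 0.92 or 0.96 instead of 0.90, for correlations of 0.1, 0.3 or 0.5, against a loss below 0.01 if there is no correlation. The overall contrast is strong when both effects are real (about 0.99). When only one is, its power runs from 0.42 to 0.84 (bone) or from 0.78 down to 0.33 (soft tissue) as bone SD goes from one to three times soft tissue SD. It therefore cannot replace the stratum analyses. All these figures rest on an assumed two-sided 0.05 and on correlations and SD ratios that the plan does not give. The transfusion gap depends on none of them.

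**What to change.** In II.C and V.A:

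1. Compare TXA with no TXA within each stratum (groups 1 v 2 and 3 v 4) by ANCOVA of hemoglobin-balance blood loss on assignment and preoperative hemoglobin, with 95% CI. Show preoperative hemoglobin descriptively by arm instead of testing it. Add blood loss to the II.C outcome list so that it matches V.A.
2. Add one overall TXA effect adjusted for stratum and preoperative hemoglobin, as a supportive estimate with 95% CI and no separate claim of significance. If it were also read at 0.05 beside two unadjusted stratum tests, the chance of some false positive would rise from 0.0975 to about 0.11. First reconcile the II.B and II.C descriptions of the stratification factor.
3. Analyse the transfusion rate as the proportion transfused, by stratum and as a Mantel-Haenszel risk difference with 95% CI. Keep units transfused as a separate outcome.
4. Keep drain output as a named secondary outcome; it is hypothesis 3.

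Stating alpha, and limiting each stratum's claim to its tumour type, would be a useful clarification.

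The cost is wording, plus one degree of freedom per stratum (under 0.01 of power at worst). The stratum, preoperative hemoglobin and transfusion incidents are already recorded, and enrolment is unchanged.

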- Vulnerable populations as defined by the University of Kansas Medical Center IRB

Withdrawal/Termination criteria: The subject's participation will be terminated by the investigator if the subject wishes to withdrawal from the study at any point in time. In the event that a disproportionate number of complications are occurring in one of the study groups, the study will be suspended and the IRB will be consulted. There are no

safety precautions that need to be applied to subjects who withdraw from the study. The withdrawn patients will be routinely followed on an outpatient basis in a clinic setting.

E. Specific methods and techniques used throughout the study

1. Laboratory tests: Complete Blood Count (CBC) – the purpose of collection is to help determine the effect of TXA on hemoglobin and hematocrit levels. A CBC would be collected pre-operatively and post-operatively at 6 hours and in the mornings of postoperative days 1, 2, and 3. Patients may be discharged prior to obtaining all 4 blood draws. If a patient is discharged prior to postoperative day 3, no additional blood draw will be performed. Blood specimens will need to be collected for this test. This test is routinely ordered in the hospital setting and is the standard of care for evaluating and monitoring blood loss post-operatively.
2. Study Procedures: Describe each procedure to be used in the study, including the instruments used, time required for each procedure, cognitive assessments, etc. The patient's consented for this study and randomized to the TXA group will receive TXA while in the operating room as part of the routine administration of anesthesia. This is not technically considered a procedure.
3. Clearly indicate which procedures, tests, visits, etc., are parts of usual standard therapy and which are performed solely for research purposes. Make it clear which tests are routinely performed for clinical care but are providing data for the research (and are billable to insurance companies), and which tests are only performed for research purposes (not billable to insurance companies). Usual standard therapy: all postoperative clinic visits, pre-operative and post-operative CBC. These CBCs would be providing data for this clinical trial. No tests will be ordered that are only performed for research purposes.
4. Describe the fate of any body component: No body components will be obtained during this study.

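### Raw hemoglobin and hematocrit changes are compared between arms with no account of transfused red cells, so this supplementary comparison shrinks toward no difference if TXA reduces transfusion

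*Combined protocol and SAP*

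**What the plan says.** - **Raw change.** II.C and V.A both state that "changes in hemoglobin and hematocrit will be compared using pairwise Student T-test analysis". Neither mentions red cells given between the draws. II.E item 1 says of the CBC that "the purpose of collection is to help determine the effect of TXA on hemoglobin and hematocrit levels".
- **Draws.** II.B and II.E schedule CBCs before surgery, at 6 hours, and on the mornings of days 1 to 3, with none after discharge. The draw that defines the change is not named.
- **Primary outcome.** II.A makes perioperative blood loss the primary outcome, calculated by the hemoglobin balance method with four references. No formula is written out. The inputs are described only thus: "values will be recorded preoperatively and compared to post-operative values". The secondary outcomes are transfusion rates and drain output.
- **Analysis lists.** V.A includes hemoglobin balance among the quantities compared by t-test. The parallel list in II.C does not. Both lists include transfusion requirements, with no unit of measurement.
- **Transfusion data.** II.B says that "both intraoperative and postoperative incidents of blood transfusion will be monitored to calculate transfusion rates".
- **Transfusion practice.** Under II.B the lead institution gives postoperative red cells for hemoglobin below 7.0. Other sites are encouraged to do the same, but the treating physician decides. I.A (hypothesis 2) and V.B expect less transfusion with TXA.

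**The concern.** A transfusion raises the hemoglobin that is measured afterwards. When low hemoglobin triggers transfusion, the patients who bled most are the ones whose values are restored. If controls bleed more and are transfused more, their observed fall understates their true fall by more than in the TXA arm, and the difference between arms shrinks.

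II.E presents the CBCs as a means of judging TXA's effect on hemoglobin and hematocrit, so a reader of the results could take a small raw difference as evidence that TXA does little. A hemoglobin balance can avoid this by adding transfused hemoglobin back, but only if the amount given before the chosen draw is known and enters the formula.

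**Working it through.** **The plan's own figure.** The only quantitative statement is the sample size in II.C: "A power of 0.9 would require a total of 40 patients (20 per treatment group) be enrolled in the bony tumor group". For soft tissue tumors the same sentence sets 50 in each arm, 100 in all. Neither size can be reproduced, because alpha, sidedness, effect size, SD and the endpoint powered are not given. Assuming two-sided 0.05, the implied standardized difference is d = √(2/n) × (1.960 + 1.282):
- bone, n = 20 per arm: 0.3162 × 3.242 = 1.025
- soft tissue, n = 50 per arm: 0.2000 × 3.242 = 0.648

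These values are back-solved and do not verify the sample sizes.

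**Loss in the raw-change contrast (simulation).** Assumptions, none from the documents except the 7.0 trigger: preoperative hemoglobin mean 11 or 12 g/dL, SD 1.5; mean control fall 3 or 4 g/dL, SD 1.5, truncated at zero; a nominal TXA effect of 1.0 or 1.5 g/dL; each patient below 7.0 given enough whole units to reach 7.0 at 1 g/dL per unit; all units given before the draw. Share lost = (true − raw) / true.

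| Pre-op mean / control fall / nominal effect | Transfused, control vs TXA | True difference, g/dL | Raw difference, g/dL | Share lost |
|---|---|---|---|---|
| 12 / 3 / 1.0 | 17.3% vs 7.9% | 0.948 | 0.775 | 0.173/0.948 = 18% |
| 12 / 4 / 1.0 | 31.8% vs 17.3% | 0.989 | 0.671 | 0.318/0.989 = 32% |
| 11 / 4 / 1.0 | 49.9% vs 31.9% | 0.991 | 0.493 | 0.498/0.991 = 50% |
| 11 / 4 / 1.5 | 50.0% vs 24.0% | 1.469 | 0.787 | 0.682/1.469 = 46% |

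Every scenario moves toward no difference and none changes sign. In the last two rows, the larger true effect still gives the larger raw difference.

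**What this could do to power.** Suppose a transfusion-corrected comparison had exactly 90% power. Bias = (control rate − TXA rate) × units per transfused patient × 1 g/dL per unit. Take 40% vs 20% transfused, 2 units each and SD 1.5: bias = 0.20 × 2 × 1 = 0.4 g/dL, or 0.4/1.5 = 0.267 SD. Power = Φ(d√(n/2) − 1.960).
- Bone: d = 1.025 − 0.267 = 0.758, power 0.67.
- Soft tissue: d = 0.648 − 0.267 = 0.382 (from unrounded values), power 0.48.

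Over rates from 20% vs 10% to 60% vs 30%, 1 or 2 units, and SD 1.0 to 2.0, the bias is 0.1 to 0.6 g/dL. Power then runs from 0.87 down to 0.27 (bone) and from 0.85 down to 0.04 (soft tissue). This grid holds the SD fixed and combines the assumptions freely, so its extremes should not be taken as predictions. In the simulation transfusion also narrowed the spread, so the standardized difference fell less than the mean difference (0.645 to 0.606 in the mildest scenario, 0.662 to 0.393 in the most severe).

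**Primary outcome, only if nothing is added back.** Assume 50 to 60 g hemoglobin per unit and preoperative hemoglobin of 100 to 130 g/L. One uncredited unit hides 50/130 = 0.385 L to 60/100 = 0.60 L of blood loss. The same grid gives a between-arm gap of (0.20 − 0.10) × 1 = 0.1 to (0.60 − 0.30) × 2 = 0.6 units per patient. That hides 0.1 × 385 ≈ 39 mL to 0.6 × 600 = 360 mL of the difference.

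**The case against.** The strongest reply is that raw change is neither a primary nor a secondary outcome in II.A, nor one of the three hypotheses in I.A. Describing hemoglobin under actual care, transfusions included, is legitimate. It misleads only when read as a measure of blood loss. That is right, and it is why labelling the comparison descriptive would be enough. But II.E ties these CBCs to TXA's effect, and neither analysis list marks raw change as descriptive.

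Three stronger readings are tempting, and the documents do not support them.

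- *The primary result is biased.* II.A names the hemoglobin balance method and V.A analyses it. Whether the cited version adds transfused hemoglobin back cannot be settled from these documents. What can be said is that the formula, the draw and the transfusion term are not written down.
- *Transfusions are recorded only as yes or no.* II.B does speak of incidents, but for calculating rates. Transfusion requirements are compared by t-test, which suggests a quantity, and II.G takes endpoint data from electronic records, with nothing limiting what is extracted. What is missing is a statement that units or volume and time are captured and used.
- *The comparison could favour control, or look worse the better TXA works.* No calculation shows this. The simulations gave attenuation only.

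The direction itself is conditional. Surgeons are unblinded and transfusion is discretionary at other sites, so transfusion need not track hemoglobin equally in both arms. If the 6-hour draw is used, some postoperative units may come after it and the effect would be smaller.

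**Conclusion.** The concern holds for the raw hemoglobin and hematocrit comparison. As planned, and if TXA does reduce transfusion, that comparison understates the TXA effect. The illustrative loss is about 18% to 50% of the true hemoglobin difference, without reversal. This rests on assumed baseline values, falls and response per unit, on transfusion at 7.0 in both arms, and on all units preceding the draw. The documents give no rates, units or timing from which to narrow the range.

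For the primary outcome the finding is a gap in specification. A reader might infer that the blood-loss result is understated in transfused patients, but that follows only if transfused hemoglobin is left out of the balance, which the documents neither say nor exclude. The gap should still be closed before analysis: investigators are unblinded, and a formula or draw chosen after the data are seen would be open to challenge. The omission of hemoglobin balance from II.C adds to the ambiguity, since on that section alone raw change is the only hemoglobin-based comparison.

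**What to change.** - **II.C and V.A:** replace the raw-change comparison with one that adds back hemoglobin transfused before the draw used. Alternatively, keep raw change but label it descriptive and not evidence on TXA efficacy.
- **II.C:** list hemoglobin-balance blood loss, as V.A does.
- **II.B:** record units or volume, and the date and time, of every intraoperative and postoperative red cell transfusion and of any salvaged blood returned.
- **II.A:** write out the hemoglobin balance formula, state that transfused hemoglobin is added, and name the postoperative draw used.

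The cost is a few fields from the transfusion record and one line of calculation, with no new test or visit. The drawback is that a standard hemoglobin content per unit must be assumed. It should be fixed in advance, and the result can be checked over a plausible range such as 50 to 60 g.
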